Appendix 2: eTICI Scale

Grade	Short description	Long description
0	No perfusion	No antegrade flow beyond the point of occlusion.
1	Minimal perfusion	The antegrade flow passes the area of obstruction but there is
		little or slow reperfusion flow in the distal branches.
2a	Reperfusion <50%	Antegrade flow fills less than 50% of the ischemic areas of
		target vessel occlusion (e.g., 1 important branch of the middle
		cerebral artery and its territory).
2b	$50\% \le \text{Reperfusion} < 90\%$	Antegrade flow fills more than 50% of the ischemic areas of
		target vessel occlusion (e.g., 2 important branches of the middle
		cerebral artery and their territories).
2c	Reperfusion ≥90%	Reperfusion antegrade flow almost completely fill the whole
		ischemic areas of the target vessel occlusion, with only slow
		flow or thrombus in a small portion of the distal vessel branches.
3	100% reperfusion	Reperfusion antegrade flow completely fill the whole ischemic
		areas of the target vessel occlusion, with no visible occlusion in
		the distal branches.

Appendix 3: EQ-5D Health-Related Quality of Life Scale

Date of score: ///// (DD/MM/YYYY)		
Item	Score	
	I have no problems in walking about	
	I have slight problems in walking about	
Mobility	□ I have moderate problems in walking about	
	□ I have severe problems in walking about	
	□ I am unable to walk about	
	□ I have no problems washing or dressing myself	
	□ I have slight problems washing or dressing myself	
Self-care	□ I have moderate problems washing or dressing myself	
	□ I have severe problems washing or dressing myself	
	□ I am unable to wash or dress myself	
	□ I have no problems doing my usual activities	
Usual activities	I have slight problems doing my usual activities	
	□ I have moderate problems doing my usual activities	
	□ I have severe problems doing my usual activities	
	□ I am unable to do my usual activities	
	□ I have no pain or discomfort	
Pain/Discomfort	I have slight pain or discomfort	
	I have moderate pain or discomfort	
	□ I have severe pain or discomfort	
	□ I have extreme pain or discomfort	
Anxiety/Depression	□ I am not anxious or depressed	
	□ I am slightly anxious or depressed	
	□ I am moderately anxious or depressed	
	□ I am severely anxious or depressed	
	□ I am severely anxious or depressed	
Status that best describes your	Sector (0.100)	
health	Score (0-100)	

16 References

- [2]. 王陇德,常继乐,张宗久. 中国脑卒中防治报告(2019). 人民卫生出版社. 2020

Appendix 2: eTICI Scale			
Appendix 3: EQ-5D Health-Related Quality of Life Scale			

LIST OF ABBREVIATIONS AND DEFINITIONS OF TERMS

Abbreviation	Definition of terms
AE	Adverse Event
AIS	Acute Ischemic Stroke
BGC	Balloon Guide Catheter
CI	Confidence Interval
CRF	Case Report Form
DSA	Digital Subtraction Angiography
DSMB	Data and Safety Monitoring Board
GCS	Glasgow Coma Scale Score
EQ-5D	EuroQol-5 Dimensions
eCRF	Electronic Case Report Form
eTICI	Extended Thrombolysis in Cerebral Infarction
ITT	Intention-to-Treat Population
LVO	Large Vessel Occlusion
MedDRA	Medical Dictionary for Drug Regulatory Activities
MRI	Magnetic Resonance Imaging
mRS	Modified Rankin Scale
NIHSS	National Institute of Health stroke scale
OR	Odds Ratio
PPS	Per-protocol Set
РТ	Preferred Term
SAE	Serious Adverse Event
SAP	Statistical Analysis Plan
SOC	System Organ Class

1 INTRODUCTION

This Statistical Analysis Plan (SAP) is developed based on the most recent study protocol (Version 4.0, 25-Oct-2023) and electronic Case Report Form (eCRF, Version 1.2, 07-Nov-2023), and details the statistical analysis strategies and methods for the study.

The SAP predefines the statistical analysis population, analysis variables and analysis methods before database lock to ensure the reliability of the study results.

1.1 Study Design

This is a prospective, multicenter, randomized controlled, open-label, blinded outcome assessment trial involving 1,074 eligible subjects with acute ischemic stroke (AIS) due to anterior circulation large vessel occlusion (LVO) to be recruited from 40-60 hospitals in China. Subjects who meet the eligibility criteria will be randomized to either intervention group (receiving treatment with balloon guide catheter [BGC]) or control group (receiving treatment with conventional guide catheter). Follow up visits will be conducted at 1 day, 7 days, and 90 days after thrombectomy. Study design is presented as below (Figure 1):

Figure 1. Study schema

1.2 Study Objectives

The objective of this study is to determine the effectiveness of BGC as compared to conventional guide catheter on functional outcome (modified Rankin Scale [mRS]

score) in patients with acute ischemic stroke due to anterior circulation large vessel occlusion.

1.3 Study outcomes

Primary efficacy outcome:

• The primary outcome is functional outcome, defined as the mRS score shift at 90 days (± 14 days).

Secondary efficacy outcomes:

- Dichotomized mRS at 90 days after the procedure (0-1 vs. 2-6, 0-2 vs. 3-6, 0-3 vs. 4-6, 0-4 vs. 5-6, 0-5 vs. 6);
- Change in stroke severity (The National Institutes of Health Stroke Scale [NIHSS] score, the criteria for scoring are detailed in Appendix 1) at 24 hours post treatment;
- Change in stroke severity (NIHSS score) at 7 days post treatment or discharge (whichever occurs first);
- Final infarction volume;
- Technical success rate (defined as successfully navigating the guide catheter into the target vessel, and finishing the mechanical thrombectomy procedure without changing to another guide catheter);
- Reperfusion outcome (Extended Treatment In Cerebral Ischemia [eTICI] 2b or greater, eTICI 2c or greater, eTICI 3; eTICI criteria are detailed in Appendix 2) in final angiogram;
- Reperfusion outcome (eTICI 2b or greater, eTICI 2c or greater, eTICI 3) after the first pass;
- Time from groin puncture to successful reperfusion (eTICI 2b or greater, eTICI 2c or greater);
- Percentage of subjects with acceptable revascularization quality (eTICI 2b or greater, eTICI 2c or greater) within 45 min of access;
- Number of thrombectomy attempts (final) ;
- Occurrence of emboli to a new territory.

Safety outcomes:

- Deaths at 90 days (±14 days) post treatment ;
- Intracranial hemorrhage, symptomatic intracranial hemorrhage or asymptomatic intracranial hemorrhage at 7 days post treatment or discharge, whichever occurs first;
- Other serious adverse events (SAEs) adjudicated by the Clinical Events Committee;
- Any peri-procedural complications, including vessel dissection, arterial perforation, and femoral access complications, etc.

Cost Outcomes:

- Health-related quality of life using EuroQol-5 Dimension [EQ-5D] (Appendix 3);
- Utility-weighted mRS scores;

- Duration of hospitalization;
- Treatment cost.

1.4 Estimation of Sample Size

In a meta-analysis ^[1] comparing BGC with conventional guide catheter, the use of balloon guide catheter improved the proportion of functional outcome by 10.8%. In this study, based on a more conservative estimate, we assume the usage of BGC would improve the function outcome by 8%. Based on the distribution of the mRS in the control group of the trial, which we derived from the intervention group of the MR CLEAN trial : mRS0: 3%; mRS 1: 9%; mRS 2: 21%; mRS 3: 18%; mRS 4: 22%; mRS 5: 6% and mRS 6:21%. We assumed a favorable treatment effect with a common odds ratio (cOR) of 1.43, corresponding to an 8% absolute increase in the rate of mRS scores of 0-2. In a simulation with 5000 runs we computed the proportion of positive trials, for a given sample size. A sample size of 1074 subjects is estimated to be able to demonstrate this treatment effect with 87% power and 5% type-1 error. This sample size also allows for 5% dropout rate and 5% crossover rate.

1.5 Randomization and Treatment allocation

Subjects will be randomized via an internet-based randomization system in a 1:1 manner to treatment with BGCs (Intervention group) or not (Control group), stratified by site, preferred initial thrombectomy strategy (stent retriever vs. aspiration vs. stent retriever + aspiration), and onset to randomization time (<6 hours vs. \geq 6 hours). The randomization sequence will use a minimization algorithm to ensure balance in these key prognostic factors. Randomization is allowed when large vessel occlusion has been established.

Subjects will be treated with thrombectomy based on the results of randomization:

- Intervention group: Subjects treated with BGCs combined with conventional thrombectomy.
- **Control group**: Subjects treated with conventional guide catheter combined with conventional thrombectomy.

Any National Medical Products Administration (NMPA) approved devices (including thrombectomy stent, aspiration catheter, or combined use of both) are allowed in this study.

1.6 Study Procedure

Before starting the study, patients or their guardians must read and sign the informed consent approved by the current Ethics Committee (EC). All research steps should be carried out within the time window specified in the study protocol.

The study consists of a total of 4 visits per subject, including: visits at baseline (pre-procedure ~ the day of treatment), 1 day (\pm 12 hours) post treatment, 7 days (\pm 2 days) post treatment or at discharge, and 90 days (\pm 14 days) post treatment.

_

The study procedure is shown in the table 1 below.

Tał	ole 1.	Schedule	of tł	ne stud	y pro	cedures

Procedure/Time Window	Baseline	1 day post treatment	7 days post treatment [#]	90 days post treatment
	Pre-operation - the day of treatment*	± 12 hours	± 2 days	± 14 days
Informed consent	Х			
Demographics	Х			
Medical history	Х			
Vital signs	Х	Х	Х	
Blood routine test	Х	Х		
Blood biochemistry	Х	Х		
Coagulation function test	Х	Х		
Imaging examination	Х	Х	Х	
mRS score	Х			Х
GCS score	Х	Х	Х	
NIHSS score	Х	Х	Х	
Quality of life using EQ-5D				Х
Inclusion/exclusion criteria evaluation	Х			
Randomization and thrombectomy treatment	Х			
Medical cost			Х	Х
Safety evaluation	Х	Х	Х	Х
Concomitant medication X		Х	Х	Х

Notes: #: at discharge or 7 days post treatment, whichever occurs first. *: The end date of surgery will be considered as the day of surgery.

2 STATISTICAL ANALYSIS METHODOLOGY

2.1 Statistical Analysis Variables

This statistical analysis plan (SAP) will include variables to be analyzed as follows: demographics and baseline characteristics, treatment efficacy and safety data.

2.1.1 Demographics and baseline characteristics

The demographic and baseline information will include age (years), sex, nationality, height (cm), weight (kg), medical history, smoking and drinking history, baseline medications, imaging examination, mRS score, NIHSS score and GCS score.

2.1.2 Efficacy outcomes

2.1.2.1 Primary efficacy outcome- mRS score

The modified Rankin Scale (mRS) is an ordinal hierarchical scale ranging from 0 to 5, with higher scores indicating more severe disability. In addition, a score of 6 is added to signify death; the criteria for scoring are detailed in Table 2:

Score	Definition
0	No symptoms
1	Symptoms, no disability: Minor symptoms that do not interfere with lifestyle
2	Slight disability: Slight disability, symptoms that lead to some restriction in lifestyle, but do not interfere with the patient's capacity to look after himself
3	Moderate disability: Moderate disability, symptoms that significantly restrict lifestyle and prevent totally independent existence
4	Moderately severe disability: Moderately severe disability, symptoms that clearly prevent independent existence though not needing constant attention
5	Severe disability, totally dependent patient requiring constant attention day and night
6	Death

Table 2. Modified Rankin Scale

The mRS score collected at 90 ± 14 days post treatment will be blindly evaluated by an independent Outcome Assessment Committee.

2.1.2.2 Secondary efficacy outcomes

- Dichotomized mRS of 0-1 vs. 2-6 at 90 days (\pm 14 days);
- Dichotomized mRS of 0-2 vs. 3-6 at 90 days (\pm 14 days);
- Dichotomized mRS of 0-3 vs. 4-6 at 90 days (\pm 14 days);

- Dichotomized mRS of 0-4 vs. 5-6 at 90 days (\pm 14 days);
- Dichotomized mRS of 0-5 vs. 6 at 90 days (\pm 14 days);
- Change in stroke severity (NIHSS score) at 24 hours post treatment;
- Change in stroke severity (NIHSS score) at 7 days post treatment or discharge, whichever occurs first;
- Final infarction volume (mL);
- Technical success rate;
- Reperfusion outcome(eTICI 2b or greater, eTICI 2c or greater, eTICI 3) in final angiogram;
- Reperfusion outcome(eTICI 2b or greater, eTICI 2c or greater, eTICI 3) after the first pass;
- Time from groin puncture to successful reperfusion(eTICI 2b or greater, eTICI 2c or greater);
- Percentage of subjects with acceptable revascularization quality (eTICI 2b or greater, eTICI 2c or greater) within 45 min of access;
- Number of thrombectomy attempts (final)
- Occurrence of emboli to a new territory

NIHSS Scale

The NIHSS is an ordinal hierarchical scale used to evaluate the severity of stroke by assessing the patient's physical strength. Scores may range from 0 to 42, with higher scores indicating more severe ischemia. Scale items includes level of consciousness, level of consciousness questions, loc commands, best gaze, visual, facial palsy, motor arm, motor leg, limb ataxia, sensory, best language, dysarthria, extinction and inattention (the criteria for scoring are detailed in Appendix 1).

NIHSS scores assessment will be collected at baseline, 24 ± 12 hours and 7 ± 2 days post treatment.

eTICI Scale

The eTICI classification includes 0, 1, 2a, 2b, 2c and 3 (eTICI criteria are detailed in Appendix 2).

eTICI grading will be collected before and after treatment.

Technical success rate

The technical success rate is defined as successfully navigating the guide catheter into the target vessel, and finishing the mechanical thrombectomy procedure without changing to another guide catheter.

2.1.3 Safety

2.1.3.1 Adverse events (AEs)

This study focused on the SAEs and peri-procedural complications adjudicated by the Clinical Events Committee.

All SAEs terms will be coded using MedDRA 25.0 or higher before study database lock. MedDRA System Organ Class (SOC) and Preferred Term (PT) will be presented in the summary tables.

Definition of SAEs

Any SAEs that occurs during the study will be recorded by the investigator from the time that the study treatment is started for the subject. According to the WHO International Centre for Drug Monitoring (1994), SAEs is defined as any of the following untoward medical events which:

- 1) Results in death;
- 2) Is life threatening in the view of the principal investigator (i.e. its occurrence places the patient or subject at immediate risk of death. It does not include an adverse event, had it occurred in a more severe form, might have caused death);
- 3) Requires inpatient hospitalization or prolongation of existing hospitalization;
- 4) Results in a persistent or significant disability or incapacity;
- 5) Result in congenital anomaly or birth defects;
- 6) Important medical events that may not result in death, be life-threatening, or require hospitalizations but may jeopardize the subject and may require medical or surgical intervention to prevent one of the outcomes listed above according to the principal investigator.

Classification by relationship of SAEs to the study device/procedure

Relationship between SAEs and study device/procedure, the investigator will evaluate the possible association between adverse events and study device/procedure according to the time relationship and its clinical judgment in terms of "definitely related", "possibly related", "definitely unrelated", "unlikely related" and "unable to determine". Among which, events whose causal relationship is judged as "definitely related" or "possibly related" will be considered as related to the study device or procedure. If a relationship to the study device or procedure was missing, the analysis was considered to be related to the study device or procedure when appropriate.

Definition of peri-procedural complications

Peri-procedural complications for this study refers to complications at time of discharge or 7 days post-randomization, which include procedural complications, procedure related complications, etc., such as vessel dissection, arterial perforation, and femoral access complications.

Classification by relationship of peri-procedural complications to the study device/procedure

Relationship between peri-procedural complications and study device/procedure, the investigator will evaluate the possible association between adverse events and study device/procedure according to the time relationship and its clinical judgment in terms of "definitely related", "possibly related", "definitely unrelated", "unlikely related" and "unable to determine". Among which, events whose causal relationship is judged as "definitely related" or "possibly related" will be considered as related to the study device or procedure. If a relationship to the study device or procedure was missing,

the analysis was considered to be related to the study device or procedure when appropriate.

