6.1.3 Safety Outcomes

- 1) Deaths at 90 days (± 14 days) post treatment;
- 2) Intracranial hemorrhage, symptomatic intracranial hemorrhage or asymptomatic intracranial hemorrhage at 7 days post treatment or discharge (whichever occurs first);
- 3) Other serious adverse events (SAEs) adjudicated by the Clinical Events Committee;
- 4) Any peri-procedural complications, including vessel dissection, arterial perforation, and femoral access complications, etc.

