- 12. Inclusion/exclusion criteria evaluation: Subjects will be evaluated for eligibility using the inclusion and exclusion criteria after signing the informed consent form, to determine whether they can be randomized;
- 13. **Randomization and thrombectomy treatment:** Subjects will be randomized to the intervention group and the control group at the ratio 1:1 after confirming the eligibility, and receive thrombectomy treatment in the intervention group or control group according to the result of randomization. Information related to thrombectomy treatment will be collected and recorded, which include but not limited to: information of product used for embolectomy, technical success rate, reperfusion outcome in final angiogram and after the first pass, time from femoral artery puncture to successful reperfusion, revascularization quality within 45 minutes, mechanical embolectomy attempts (final), and occurrence of emboli to a new territory, etc.;
- 14. **Safety evaluation:** All-cause death, intracranial hemorrhage, other SAEs, and procedure-related complications during the study will be collected;
- 15. **Concomitant medication:** including thrombolytics, anticoagulants, antiplatelets, blood pressure/lipid and blood glucose control medications taken by the subjects during the study, and concomitant medications associated with any SAE.

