6.2.2.4 Visit 4: 90 days (±14 days) post treatment

- 1) mRS;
- 2) Quality of life evaluation using EQ-5D;
- 3) Medical cost;

- Safety evaluation: All-cause death, intracranial hemorrhage, other SAEs, and procedurerelated complications experienced by subjects during the study will be collected;
- 5) Concomitant medication: Thrombolytics, anticoagulants, antiplatelets, blood pressure/lipid and blood glucose control medications taken by the subjects during the study, and concomitant medications associated with any SAE will be collected.

7 Statistical Analysis

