10.1.3 Recording and Follow up of Adverse Events

The investigator or authorized staff will document serious adverse events and procedure-related complications occurring at any time during the study after the subject has signed the informed consent form. Any serious adverse event or procedure-related complication should be treated and followed up until the event has been reasonably resolved (e.g. symptoms recovered, resolved, or reach to a stable state, or can be well-explained). All treatments and results for SAEs and procedure-related complications must be documented appropriately on the CRF.

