2.3.6.1 Analysis of AEs

The number and percentage of subjects who had at least one serious adverse event, classification of serious adverse event, adverse events of intracranial hemorrhage and symptomatic intracranial hemorrhage or asymptomatic intracranial hemorrhage at 7 days post treatment or discharge.

- All SAEs will be summarized by SOC and PT;
- Any peri-procedural complications will be summarized by SOC and PT.

In order to signal potential safety problems, comparisons of the frequency of SAEs and peri-procedural complications between treatment groups will be performed by using a Chi-squared test or Fisher's exact test when appropriate.

The data listings will be provided for All SAEs, any procedural complications and deaths at 90 days post treatment.

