3 CHANGES TO PLANNED ANALYSES FROM THE PROTOCOL

No changes of planned analyses in the protocol are made in this statistical analysis plan.

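### The SAP window for peri-procedural complications closes at discharge, and non-serious complications after the cut-off enter no planned comparison between arms

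*SAP*

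**What the plan says.** Protocol 6.1.3 lists the safety outcome as "Any peri-procedural complications, including vessel dissection, arterial perforation, and femoral access complications, etc" and attaches no time window, although deaths and intracranial hemorrhage in the same list are timed. Under Protocol 10.1.3 the investigator or authorised staff "will document serious adverse events and procedure-related complications occurring at any time during the study". Note 14 to the schedule in Protocol 6.2.1 reads "All-cause death, intracranial hemorrhage, other SAEs, and procedure-related complications during the study will be collected", and Protocol 6.2.2.4 repeats the item for the day-90 visit: "Safety evaluation: All-cause death, intracranial hemorrhage, other SAEs, and procedurerelated complications experienced by subjects during the study will be collected".

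SAP 2.1.3.1 then narrows the outcome: "Peri-procedural complications for this study refers to complications at time of discharge or 7 days post-randomization". The same sentence says that procedure-related complications are included. SAP 2.3.6.1 states "Any peri-procedural complications will be summarized by SOC and PT" and plans a chi-squared or Fisher's exact test between arms for SAEs and for peri-procedural complications. SAP 3 states "No changes of planned analyses in the protocol are made in this statistical analysis plan".

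**The concern.** Two things stand out. First, the SAP sets a cut-off that the protocol outcome does not have, on a category of event that the protocol collects to day 90, and SAP 3 does not mention it. Secondly, the cut-off is not one clear rule. The intracranial hemorrhage outcome is anchored on treatment and says that the earlier of day 7 and discharge applies. The complication definition is anchored on randomization and has no such clause.

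The outcome matters because complications are a harm that the protocol itself links to the device: its background section says that the stiffness and trackability of the balloon catheter may cause them. If counting stops at discharge, observation ends at an event that follows randomization and that treating physicians, who know the allocation, can influence. Duration of hospitalization is itself a trial outcome. If one arm went home sooner, it would have less time in which a complication could be counted.

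**Working it through.** No design figure is involved, so the check is a comparison of the passages and of the windows they imply.

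**1. Length of the windows.** Counting under the SAP stops at day 7 or at discharge. Collection runs to the day-90 visit, with a margin of 14 days: 90 − 14 = day 76 to 90 + 14 = day 104. Collection after day 7 therefore lasts 76 − 7 = 69 to 104 − 7 = 97 days, ignoring the short gap between randomization and treatment. It lasts longer for a patient whose window closes at an earlier discharge.

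**2. What the SAP wording can mean.** Three illustrative patients, each with a non-serious complication:

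| Patient | Earlier of the two | Day 7 only | Discharge only | Later of the two |
|---|---|---|---|---|
| Discharged day 3, event day 6 | not counted | counted | not counted | counted |
| Discharged day 15, event day 12 | not counted | not counted | counted | counted |
| Discharged day 10, event day 40 | not counted | not counted | not counted | not counted |

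The first two patients change with the reading; the third is left out under all of them. SAP 2.4.3, on time windows, says only that it is not applicable, so it does not settle the matter. The footnote to the visit schedule (Protocol 6.2.1 and SAP 1.6) defines the day-7 visit as the earlier of discharge and day 7. That makes the first column the likely reading.

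**3. Time at risk under the likely reading.** The window lasts min(day of discharge, 7). A patient discharged on day 4 contributes 4 days; one discharged on day 7 or later contributes 7. Time at risk thus depends on length of stay.

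**4. Where a complication after the cut-off is reported.**

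- *It meets an SAE criterion.* SAP 2.1.3.1 records SAEs throughout the study. SAP 2.3.6.1 tabulates all of them by SOC and PT and compares their frequency between arms, with no day-7 or discharge limit. The event is counted.
- *It is not serious.* It falls outside the complication table and its test, and outside the SAE table and its test. SAP 2.3.6.1 also promises a listing of procedural complications with no stated cut-off, so the event may appear there, but a listing compares nothing.

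**5. Number affected.** Neither document gives a complication rate, a distribution of onset times or a length of stay by arm, so the count cannot be derived.

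**The case against.** The strongest defence is that the term peri-procedural already implies a short period around the procedure. Protocol 7.2 leaves analysis detail to the SAP, and collecting events more widely than one outcome counts them is not a contradiction. This stands: an early window is not in itself an error. It does not cover the whole point, because the SAP's own definition takes in procedure-related complications, the item the protocol collects to day 90.

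The schedule footnote largely settles which end point governs. The randomization anchor should also matter little, since thrombectomy is to take place within 24 hours of onset. Both points stand, but the likely reading is the one that closes at discharge. The protocol uses a discharge-dependent window for hemorrhage and for the later NIHSS score too; for complications, however, the protocol sets no such window.

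Three stronger readings are tempting, and the documents support none of them:

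- *Late complications are collected but not counted.* This is untrue of those that are SAEs.
- *The window biases the harm comparison.* It could, but no document shows that length of stay differs by arm. A complication that prolongs the hospital stay is an SAE and is counted regardless. SAP 2.3.6 describes the safety analysis as mainly descriptive.
- *Several events per arm are lost.* One might assume that 5–10% of the 537 patients per arm have a complication and that 10–30% of those occur late, which gives 537 × 0.05 × 0.10 = 2.7 to 537 × 0.10 × 0.30 = 16.1. Neither rate stands in the documents, and the product includes SAEs that are still compared. It is not an estimate of the loss.

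**Conclusion.** The point holds as a minor one. The planned between-arm comparison of peri-procedural complications rests on a window that the protocol does not state, whose end point is not fully specified and which probably closes at discharge. Non-serious procedure-related complications after that cut-off, although recorded, enter no planned comparison. The size is unknown and probably small: the complications named in the outcome are tied closely to the procedure, and serious late events are captured elsewhere. The primary analysis is not affected.

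The conclusion assumes that the schedule footnote governs the complication window. If discharge alone or the later of the two points were meant, the dependence on discharge would remain; if day 7 alone were meant, it would disappear. In every case late non-serious events would still be left out of the comparison.

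**What to change.** In SAP 2.1.3.1 and 2.3.6.1, count complications over one fixed window from the start of the procedure, for example to day 7, in both arms and regardless of discharge. Add one by-arm table and comparison of all procedure- or device-related complications recorded up to the day-90 visit. The day-90 total need not replace the early window as the main definition. Enter the window in SAP 3 as a specification that the protocol does not contain.

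The cost is a few lines of SAP wording and one extra table before database lock. No new data are needed, provided that the eCRF holds an onset date for each complication, which the documents do not state outright. The only downside is that complication rates may come out slightly higher in both arms.
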